This proposal involves a pragmatic multi-site clinical trial of an early intervention with this at-risk population of Veterans: Screening, Brief Intervention and Referral to Treatment for Pain Management (SBIRT-PM). SBIRT-PM aims to engage Veterans applying for compensation with pain conditions in multi-modal non-pharmacological pain care and to motivate those who misuse substances to change this problematic behavior.

SBIRT-PM will be delivered centrally by telephone throughout the New England VA Healthcare System’s (VISN1) eight medical centers using a hub-and-spoke network implementation strategy guided by a Relational Coordination Framework. Hub-based SBIRT-PM counselors will coordinate Veterans’ engagement in non-pharmacological pain services through interactions with the extant spoke site personnel who refer Veterans to pain and/or substance abuse treatment. In this pilot trial, we will enroll five veterans from each of the eight medical centers in New England. Enrolled participants will be assessed at baseline and week 12. After baseline, they will be contacted by a study counselor and offered SBIRT-PM, a telephone-based initial session followed by up to three calls in a 12-week period to support Veterans engagement in non-pharmacological pain care.

Our first objective is to plan and prepare the multi-site pragmatic trial of SBIRT-PM vs. UC for implementation. The specific aims are to:

Aim 1: Secure VA Central IRB approval for the multi-site protocol (milestone: approved protocol).

Aim 2: Prepare SBIRT-PM for implementation at each site by (a) conducting key informant interviews about SBIRT-PM, (b) establishing procedures at the spokes to communicate contact information for Veterans applying for compensation to the study recruiter, (c) visiting sites to better coordinate SBIRT-PM between hub and spoke sites, and (d) piloting the intervention. Milestones for achieving these are completed interviews and qualitative thematic analysis of the transcribed interviews; site-specific recruitment procedures detailed in standard operating procedures; site visits completed; pilot SBIRT-PM with up to 10 Veterans per site; site-specific adjustments made to SBIRT-PM to facilitate pain treatment referrals.

Aim 3: Refine new outcome measures (milestones: worksheet for estimating costs; natural language processing algorithm to identify use of specific pain services).

UG3 2-year Planning Phase Milestones

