[name] will train two counselors at VA Connecticut (the hub) in SBIRT-PM. He will use well-established methods used to train MI-based brief interventions to counselors in several other multi-site clinical effectiveness and counselor training trials.(97-101) In brief, this will entail an 8-hour experiential workshop and SBIRT-PM manual review, followed by supervised pilot cases at each of the sites, incorporating fidelity rating-based feedback and coaching based on the review of audio recorded telephone sessions using the Independent Tape Rater Scale.(102) [name] will conduct the supervision and meet with the counselors on a biweekly basis during the preparation phase. Beyond developing their SBIRT-PM proficiency, [name] will discuss with the counselors their efforts to coordinate Veteran referral to and engagement in non-pharmacological pain management services with primary care providers. In addition, he will track the minutes counselors spend conducting the session to determine the optimal length when delivered by telephone instead of in-person (as was done in the completed SBIRT-PM trial). [name] will log observations generated from supervision and his session reviews to inform adjustments to SBIRT-PM delivery, including the coordination of relationships between the counselors and site providers and administrators. He will share these observations with the SBIRT-PM research group.

We will pilot SBIRT-PM with up to 10 Veterans at each site (total up to n=80) who meet trial eligibility criteria. We will qualitatively assess the Veterans' reactions to the intervention within each site, as described above. This information will be used to adjust SBIRT-PM prior to trial implementation. All data will be shared with the SBIRT-PM research group, where ongoing revisions to the SBIRT-PM therapy manual will be made.

12. Pilot pragmatic trial procedures at each site and finalize standard operating procedures

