Recruitment, informed consent, baseline and 12-week follow-up assessment methods will be piloted with the 10 pilot SBIRT-PM Veterans at each site. In addition, we will pilot both the nail sample and blood spot collection procedures to allow the research team to determine which approach is the most feasible for gathering drug/ethanol use metabolites in the UH3 Phase. Data management and quality monitoring systems will be tested. Any problems with trial procedures will be corrected. The Project Director will draft all trial standard operating procedures, which Drs. [name] and [name] will review and edit before final approval.

13. Develop a new natural language processing (NLP) algorithm that identifies use of non-pharmacological pain management services with a positive predictive value of at least 0.7 (validated against expert rating of chart notes)

To comprehensively identify pain-related treatment delivered to study participants, we will validate and extend existing natural language search algorithms, using previously-described procedures, to identify current use of a comprehensive set of pain treatments including those *not covered by the existing algorithms*. Those modalities will be drawn from a review of modalities used by Veterans for pain treatment and those offered in VISN 1 (see Preliminary Studies). Algorithm development will be informed by our prior experience with this study design. We will design algorithms to maximize positive predictive value (at the expense of sensitivity) to avoid the risk of including false positives that are not randomly distributed (e.g., refused treatment referrals). The NLP extraction target will be current use of the modality. Particular attention will be paid to excluding pain discussions that do not represent treatment because they were obtained in the course of routine medical history reviews. Algorithm development involves extracting relevant snippets that mention a particular pain treatment, establishing a valid classification system for current use of that pain treatment, and optimizing the machine learning algorithm to identify current use of that treatment.

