To examine feasibility of enrollment, counseling participation, and pilot study retention, descriptive data (frequency counts, percentages, means, and standard deviations) were calculated. Descriptive data were also provided for study outcomes. Changes in BPI scores and the number of nonpharmacological pain treatments utilized from baseline to week 12 were calculated and examined using the Wilcoxon signed rank sum test, the nonparametric equivalent of the paired *t*-test. The percentages of participants with problematic substance use were compared between baseline and week 12 using χ^2 tests. The *p* values should be interpreted with caution given lack of a control group and limited statistical power. For qualitative analysis, transcribed interviews were analyzed using standard qualitative analysis methods by which 2 coders independently reviewed the transcripts, creating code definitions as concepts emerged inductively from the data. Codes were refined until a final coding structure was reached, capturing the major concepts in the data, which was then applied to all transcripts.

Analysis of Qualitative Data.

We hypothesize that implementation of SBIRT-PM will be associated with changes in the way staff interact with each other, how they think about pain treatment, and how they connect service-connection claimants to treatment. To test these hypotheses, we will compare results from the Relational Coordination Survey administered before the RCT with survey results from the same participants afterwards using paired-samples *t*-tests. The comparison of semi-structured interviews with stakeholders and staff before and after the RCT will involve describing differences in themes identified at the two timepoints.

Analyses of NLP Algorithms

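### Change in problematic substance use is tested by χ² with no paired form named, although the same Veterans are measured twice; read literally, the test ignores the pairing and is conservative

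*Combined protocol and SAP*

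**What the plan says.** Under Data Analysis: "The percentages of participants with problematic substance use were compared between baseline and week 12 using" χ² tests. No form of the test is given, and no paired method for a binary outcome appears anywhere in the document.

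The data are paired. Under Specific Aims: UG3 planning phase, "Enrolled participants will be assessed at baseline and week 12". Section 12, on piloting the trial procedures, likewise says that "baseline and 12-week follow-up assessment methods will be piloted with the 10 pilot SBIRT-PM Veterans at each site". There is no comparison group, so the only contrast is within person.

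The neighbouring tests are named as paired. Changes in BPI scores and in the number of treatments used were "examined using the Wilcoxon signed rank sum test, the nonparametric equivalent of the paired" t-test. Under Analysis of Qualitative Data, the first staff survey is compared with "survey results from the same participants afterwards using paired-samples" t-tests.

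The Data Analysis section also warns that the p "values should be interpreted with caution given lack of a control group and limited statistical power".

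Two pilot sizes are stated. The Specific Aims say "we will enroll five veterans from each of the eight medical centers in New England", which is 5 × 8 = 40. Section 11 says "We will pilot SBIRT-PM with up to 10 Veterans at each site (total up to n=80) who meet trial eligibility criteria". Both sizes are used below.

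**The concern.** A Pearson χ² comparing two percentages takes its variance from two independent groups. Here each Veteran contributes to both percentages. If a Veteran with problematic use at baseline is more likely than others to have it at week 12, the true variance of the change is smaller than the one Pearson uses. The p value is then too large on average and real change is harder to detect. Substance misuse is one of the two behaviours that SBIRT-PM targets, and the section itself already calls power limited.

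The substance-use comparison is the only pre-post test in the section without a paired label, and a reader cannot tell from the documents which χ² test was run.

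**Working it through.** The plan gives no alpha, prevalence, effect size or power for this comparison, so there is no figure of its own to reproduce. What follows is conditional on the Pearson reading.

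**Inputs.** From the documents: n = 40 or 80, same Veterans at both times. Assumed: two-sided alpha 0.05; null prevalence 10% to 50%; a fall from 50% to 30% as the main alternative; phi 0, 0.3 and 0.5. The analysis section gives no cut-off for problematic use. Low prevalence is included because the ASSIST scores each substance separately.

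**1. Large-sample size of Pearson on paired data.** With equal prevalence p at both times, the true variance of the difference is 2p(1−p)(1−phi)/n. Pearson uses 2p(1−p)/n. The true size is therefore 2 × [1 − Φ(1.96/√(1−phi))].
- phi 0: 5.0%
- phi 0.3: 1.96/√0.7 = 2.34, size 1.9%
- phi 0.5: 1.96/√0.5 = 2.77, size 0.56%
- phi −0.2: size 7.4%, so conservatism depends on positive correlation

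**2. Exact type I error.** All four-cell tables were enumerated, with cell probabilities set by the two prevalences and phi; Pearson without continuity correction, prevalence 10% to 50%.

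| phi | Pearson, n=40 | mid-p McNemar, n=40 | Pearson, n=80 | mid-p McNemar, n=80 |
|---|---|---|---|---|
| 0 | 4.8–5.9% | 3.6–4.7% | 4.7–5.1% | 4.45–4.85% |
| 0.3 | 1.9–2.5% | 2.5–4.6% | 1.8–2.0% | 4.1–4.6% |
| 0.5 | 0.60–0.96% | 1.4–4.1% | 0.52–0.62% | 3.6–4.65% |

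At n=40 and prevalence 30% or 50%, asymptotic McNemar (no correction) has size 4.3% to 4.6% for phi 0.3 and 0.5.

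**3. Power for an assumed fall from 50% to 30%.**

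| n | phi | Pearson | McNemar, asymptotic | McNemar, mid-p | McNemar, exact |
|---|---|---|---|---|---|
| 40 | 0 | 46% | 45% | 42% | 35% |
| 40 | 0.3 | 45% | 57% | 57% | 48% |
| 40 | 0.5 | 43% | 73% | 72% | 63% |
| 80 | 0 | 73% | 73% | 73% | 68% |
| 80 | 0.3 | 77% | 88% | 86% | 83% |
| 80 | 0.5 | 81% | 97% | 96% | 95% |

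**4. Where the gain shrinks.** For an assumed fall from 15% to 5% at n=40:
- phi 0: Pearson 34.9%, asymptotic McNemar 29.5%, mid-p 27%
- phi 0.3: Pearson 31%, asymptotic McNemar 41%, mid-p 32%, exact 20%

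**5. One table.** Suppose 20 of 40 are positive at baseline and 12 of 40 at week 12. The pooled proportion is 32/80 = 0.4, so Pearson χ² = 0.2² / (0.4 × 0.6 × 2/40) = 0.04/0.012 = 3.33, p = 0.068, however the changes split. If 10 Veterans improved and 2 worsened (phi 0.44), McNemar χ² = (10−2)²/12 = 5.33, p = 0.021; mid-p 0.022; exact 0.039. If 12 improved and 4 worsened (phi 0.22), mid-p is 0.049 but exact is 0.077, larger than Pearson's.

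**The case against.** The strongest reply is that no error is shown. McNemar's test is itself a χ² test. The authors describe the signed rank test in paired terms just before this sentence, so they plainly knew that the data were paired. This stands: the Pearson reading is the literal one and is likely, but it is not proven. A reader might infer that the pilot's substance-use result was computed wrongly; the documents do not support that.

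A second reply is that the consequence is small. This is a single-arm pilot with descriptive aims. No decision rule rests on the test, and the section urges caution with its p values. This also stands, although the caution concerns the missing control group and limited power and does not mention pairing.

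A third reply is that McNemar's test is not always the more powerful choice. This is correct for the exact and mid-p versions when phi is near 0 or prevalence is low, and for the asymptotic version at low prevalence with n=40. It limits the claimed gain but does not make an independent-groups variance right for paired data.

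Finally, prevalence, effect and phi are all assumed. Problematic use might rest on the ASSIST (3-month recall) or the AUDIT-C (past year), and phi could differ between them. The sizes above are therefore illustrations, not estimates for this trial.

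**Conclusion.** The point holds as a minor one. The documents establish that paired binary data are compared by a test with no paired form named. Taken literally as Pearson χ², that test uses the wrong variance. Under positive correlation (assumed phi 0.3 to 0.5, n=40, prevalence 10% to 50%), its true size is about 2.5% down to 0.6%. For an assumed fall from 50% to 30%, power is 43% to 45%, where mid-p or asymptotic McNemar gives 57% to 73%. The pattern is the same at n=80.

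Two stronger readings should be resisted. One is that false positives are inflated: with positive correlation, which is plausible for the same person 12 weeks apart but not documented, the error runs the other way. The other is that a paired test would always give a smaller p value: the 12/4 split above is a counterexample for the exact version.

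**What to change.** In Data Analysis, replace the reference to χ² tests with McNemar's test among Veterans with both assessments, using the exact or mid-p version if discordant pairs are few. If McNemar's test was in fact used, saying so settles the matter. In either case, report the two discordant counts (improved and worsened) and the paired difference in percentages with a paired 95% confidence interval, so that readers can check the result under any version.

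The cost is one sentence and, if Pearson was used, a re-run on existing data. There are two downsides. Veterans without week-12 data drop out of the test. Exact and mid-p McNemar also lose some power when phi is near 0: at n=40, for a fall from 50% to 30%, mid-p has 42% against Pearson's 46%. The asymptotic version loses little or nothing there (45.0% against 45.8% at n=40; 73.1% for both at n=80), except at low prevalence with n=40 (29.5% against 34.9% for a fall from 15% to 5%).

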After motivating Veterans for engagement in pain management services, the counselor transitions to screening for substance use. The counselor explains that some people with chronic pain use various substances to help them cope with the pain and obtains the Veteran's permission to discuss this. The counselor then screens for substance use. If the Veteran reports no risky substance use, the counselor summarizes the session, reiterates the plan, and schedules the next session. If the Veteran reports risky substance use, the counselor asks more about it and how the use is affected by the Veteran's pain. The counselor provides feedback about the risky substance use, including evidence that people who don't misuse substances have significant reductions in their pain compared to those who continue to do so. As with efforts to address the Veteran's interest in pain management services, the counselor uses MI consistent approaches to motivate the Veteran to stop or reduce risky substance use. Some Veterans will not want to pursue abstinence and, for them, a harm reduction approach will be taken, meaning the counselor and Veteran will negotiate a plan to use less of the problematic substance per occasion, or use on fewer days, but not necessarily strive for abstinence. The counselor will develop a plan with the Veteran about how to reach a goal of abstinence or reduced or less frequent use, including options for engaging in specialty addiction treatment services available at the VA. When mental health issues further complicate the Veteran's pain management and risky substance use, the counselor will also discuss these issues with the Veteran. In fact, some Veterans may insist on PTSD (or depression) treatment instead of substance abuse treatment, and, consistent with MI, Veterans will receive information about preferred available treatments, including if the Veteran prefers to first talk with the primary care provider about his or her addiction or mental health concerns.

Follow-up Sessions.

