- ASSIST. Substance use will be measured over the last 3 months using Version 3.1 of the Alcohol, Smoking and Substance Involvement Screening Test (ASSIST). After a screening question focusing on substances ever used, the ASSIST consists of seven questions about use of and consequences of use of each of ten classes of substances over the preceding three months (including nicotine). Scores are generated for each substance that are mapped to a three-point ordinal scale of severity.(131) As outlined in the World Health Organization’s Manual describing the use of the ASSIST to guide treatment recommendations, the ASSIST ratings are scaled to represent no need for treatment, need for a brief intervention, and need for an intensive intervention. An advantage of the ASSIST is that these categories represent what clinicians consider a clinically important difference, in that they guide treatment recommendations. The items in the ASSIST have been shown to have good to excellent reliability for the substances assayed. The reliability of the individual ASSIST items,(132) and the ASSIST’s concurrent validity compared to other more detailed assessments of substance use severity(133) have justified its adoption by the World Health Organization.(134) We will obtain additional specifiers for substances requiring further characterization: a specifier about use of vaping for tobacco products, a specification as to whether the Veteran is using legal or prescribed cannabis and specification about use of prescribed amphetamine.
- Prescription Opioid Misuse Two questions,(135) adapted from the CIDI(136) for use in a NIDA Clinical Trials Network study,(137) will be used to describe misuse of prescribed opioid medications: “How often have you taken your pain medications in larger

amounts than prescribed or for a longer period than prescribed?" and "How often have you used your pain medicines to get high, to relax, or to make you feel more alert?" The questions are asked about the preceding 4 weeks, with follow-up questions to clarify that the question refers to opioids only.

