- Alcohol Use Disorders Identification Test (AUDIT-C)(140). This is an alcohol screen used to identify patients who are hazardous drinkers or have active alcohol use disorders (including alcohol abuse or dependence). It consists of three questions: "how often did you have a drink containing alcohol in the past year?", "how many drinks did you have on a typical day when you were drinking in the past year", and "how often did you have six or more drinks on one occasion in the past year". It is scored on a scale of 0 (no use) through 12. In men, a score of 4 or more is considered positive and in women, a score of 3 or more is considered positive.
- Prescribed Opioids or Stimulants: Certain prescribed medications will make fingernail testing results come up positive. To determine whether a positive nail toxicology result is due to illicit use or due to a prescribed medication, we will ask two questions: In the past 12 weeks have you been prescribed (1) opioid medications such as codeine, Vicodin, oxycodone, fentanyl, morphine, methadone, or suboxone? (2) Amphetamine-type stimulants such as Ritalin, Dexedrine, Adderall, Vyvanse, Concerta, or methylphenidate?"

Other Measures:

- Patient Health Questionnaire (PHQ-9): The PHQ-9 is a well validated screening measure for depression(141) and will be used to identify probable depression as a covariate in analyses. It will also identify suicidal ideation, which if severe, will trigger the need for further assessment (detailed in Human Subjects).

- EQ-5D-5L(142). The EQ-5D-5L is a standardized measure of health status designed to provide a single index value of health for clinical and economic appraisals. It consists of five questions in the domains of mobility, self-care, usual activities, pain/discomfort, and anxiety/depression
- Work Productivity and Activity Impairment Questionnaire-General Health (WPAI-GH Interviewer Versions)(143). This assessment measures the effect of general health and symptom severity on work productivity and regular activities during the past seven days. It consists of six questions. Q1 asks if currently employed. Q2 asked hours missed due to health problems, Q3 asks about hours missed for other reasons, Q4 asks about hours actually worked. Q5 asks the degree health affected productivity while working. Q6 asks the degree health affected productivity in regular unpaid activities.

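### Substance use is tested only as a yes/no percentage with no stated instrument or cut-off, so graded improvement on the ASSIST, including one clinically important step under any ASSIST cut, goes untested

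*Combined protocol and SAP*

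**What the plan says.** The Data Analysis section has one inferential comparison for substance use: "The percentages of participants with problematic substance use were compared between baseline and week 12". The method is given as "compared between baseline and week 12 using χ^2 tests", with no paired version named. The section gives no definition of problematic use. It describes the outcomes as well, without saying whether by ASSIST level or score, and warns that p values need caution because there is no control group and power is limited. BPI change and treatment counts, in the same paragraph, get the Wilcoxon signed rank test.

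Under Substance Use Measures, the ASSIST entry says: "Scores are generated for each substance that are mapped to a three-point ordinal scale of severity". The levels are explained thus: "the ASSIST ratings are scaled to represent no need for treatment, need for a brief intervention, and need for an intensive intervention". The entry counts this as an advantage of the instrument, because "these categories represent what clinicians consider a clinically important difference, in that they guide treatment recommendations". The assessment table schedules the ASSIST at baseline and week 12.

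Other measures could also supply a yes/no variable. The AUDIT-C has a threshold: "In men, a score of 4 or more is considered positive and in women, a score of 3 or more is considered positive". The nail assay has an ethyl glucuronide threshold of 8 pg/mg.

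The Initial Session section says that with Veterans who do not want abstinence the counselor will "negotiate a plan to use less of the problematic substance per occasion, or use on fewer days, but not necessarily strive for abstinence".

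**The concern.** The plan values the ASSIST for its graded, treatment-guiding categories, and the counselling aims in part at reduced use. The only test then uses a two-level variable. A Veteran who cuts down without crossing the unstated threshold counts as unchanged, even after moving a full ASSIST level.

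A small uncontrolled pilot could then report no change in substance use when its own instrument recorded improvement, and nobody could tell from the plan which improvements the test could see. Comparing two percentages from the same people as if they were independent samples makes this worse.

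**Working it through.** **Inputs from the documents.** N = 5 x 8 = 40 (Specific Aims: UG3 planning phase) or up to 10 x 8 = 80 (item 11, training and piloting). The ASSIST has three ordered levels: none, brief, intensive. The plan gives no alpha, power, baseline severity mix or expected change for this comparison, so there is no figure to reproduce. All mixes and transition rates below are assumptions, with two-sided alpha 0.05.

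**Step 1: what a cut loses.** A three-level scale has two adjacent steps, and a binary cut sees only one of them.
- Cut at brief or worse: intensive-to-brief is not counted.
- Cut at intensive: brief-to-none is not counted.
- Under either cut, a lower score within the same level is not counted.
- If the variable comes from the AUDIT-C or nail assay, no ASSIST step is tested.

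**Step 2: worked example.** Assume 40 Veterans: 20 none, 12 brief, 8 intensive. Let k of the 8 move from intensive to brief and nothing else change. For paired tests with all k changes in one direction, the exact two-sided p is 2 x 0.5^k; the sign test and signed rank test agree here, because every change is one step.

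| k | Cut at brief or worse | p | Cut at intensive | chi-square p | exact McNemar p | ordered paired p |
|---|---|---|---|---|---|---|
| 4 | 20/40 to 20/40 | 1.00 | 8/40 to 4/40 | 0.21 | 0.125 | 0.125 |
| 6 | 20/40 to 20/40 | 1.00 | 8/40 to 2/40 | 0.043 | 0.031 | 0.031 |
| 8 | 20/40 to 20/40 | 1.00 | 8/40 to 0/40 | 0.003 | 0.008 | 0.008 |

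For k = 4, the chi-square is 2 x (2²/6) + 2 x (2²/34) = 1.57, giving p = 0.21. The mirror case: if 6 of the 12 brief cases move to none, the intensive cut stays at 8/40 (p = 1.00), while the ordered paired test again gives 0.031. Only the ordered analysis sees both.

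**Step 3: power, transition model.** Assume intensive-to-brief 40%, intensive-to-none 10%, brief-to-none 30%, and worsening by one level 5% from none and from brief; 4,000 simulations per setting. The first three power columns cut at brief or worse or use the ordered levels; the last cuts at intensive.

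| N | Baseline none/brief/intensive | Unpaired chi-square | Exact McNemar | Ordered sign test | McNemar, cut at intensive |
|---|---|---|---|---|---|
| 40 | 50/40/10% | 0.04 | 0.22 | 0.28 | 0.01 |
| 40 | 40/35/25% | 0.04 | 0.24 | 0.58 | 0.24 |
| 80 | 50/40/10% | 0.12 | 0.60 | 0.61 | 0.06 |
| 80 | 40/35/25% | 0.14 | 0.69 | 0.93 | 0.69 |

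**Step 4: power, latent severity model.** Assume normal latent severity with within-person correlation 0.6 to 0.8, about 40% at brief or worse and 10% intensive, and a 0.6 SD fall only in those at risk at baseline. With N = 40:
- chi-square on the two percentages: 15-17%, with type I error about 1% or less;
- paired binary test (mid-p McNemar): 17-26%;
- Wilcoxon on three levels: 25-43%;
- Wilcoxon on a score floored at zero: 33-54% (the score scaling is a further assumption).

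Both models rank the methods the same way: unpaired binary, paired binary, then ordered levels. The second adds the score, which does best.

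**The case against.** A reader might infer that an intensive-to-brief move always counts as no change. The documents do not support that. It needs problematic use to be an ASSIST variable and the cut to lie at brief or worse, and neither is stated. With the cut at intensive, that move is the one counted. Reduced use can also take a Veteran from brief to none, which a brief-or-worse cut does register, so it would be wrong to call all harm reduction invisible.

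The strongest case for leaving the plan alone is that little hangs on this test. The pilot is uncontrolled, its analysis leads with feasibility, no planning-phase milestone depends on a substance use result, and the section already cautions about p values. The Background expects mostly episodic risky drinking without dependence, so the intensive group may be small; in the transition model the ordered test then gains little over McNemar (0.28 against 0.22 at N=40, 0.61 against 0.60 at N=80). Descriptive reporting might show ASSIST levels anyway.

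Most of this stands, and it limits the weight of the point. It does not remove it. Limited power is a reason to keep information; nothing says the description will be by level or score; and a small intensive group leaves the argument for the score intact, because reductions within the brief level appear only there. The plan's claim of clinical importance covers the categories, though, not the raw score.

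A careless remedy would also do harm. Testing each of ten substance classes multiplies tests, and a highest level that includes nicotine could hide a fall in alcohol in a Veteran whose tobacco level is unchanged.

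**Conclusion.** The point holds in this form. The only substance use test is on a yes/no percentage whose instrument and cut-off are not stated. Any ASSIST cut loses one adjacent step and all within-level change; a variable from another measure leaves the ASSIST untested. This follows from the text without a numerical assumption.

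The size does rest on assumptions. At N=40 the ordered paired test gained from 0.06 to 0.34 in power over McNemar at brief or worse (0.28 - 0.22 and 0.58 - 0.24), depending on whether 10% or 25% start at the intensive level. Ignoring the pairing cost a further 0.18 to 0.20 (0.22 - 0.04 and 0.24 - 0.04). The documents give neither the severity mix nor the expected change, and the gain from three levels is small if few Veterans are intensive. Even after the change the result stays exploratory. This is a cheap improvement that should be made, not a flaw that undermines the pilot.

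**What to change.** 1. Define problematic substance use by instrument, substance and cut-off.
2. Test within-Veteran change from baseline to week 12 in ASSIST level and score with the Wilcoxon signed rank test already used for BPI. Take alcohol first, since the Background expects mainly risky drinking, then the highest level across substances excluding nicotine. Report other substances, nicotine included, descriptively.
3. Show the 3x3 table of baseline by week-12 ASSIST level.
4. Keep the percentage as a descriptive line; if it is still tested, use McNemar.

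The cost is a few lines of analysis on data scheduled at both visits, and a couple of added exploratory tests (alcohol, and highest level without nicotine; three if alcohol is tested on both level and score). The Data Analysis section is written in the past tense, so label the added tests post hoc if the data have already been analysed.
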